7.1 TIMING OF ASSESSMENTS

An overview of the timing of treatment(s) and assessments is given in the Time and Events Schedule of the vaccination period as well as for the challenge phase.

A 10% deviation from theoretical post dose times will be allowed for all post-dose assessments. The windows for follow-up visits post-vaccination will be 7 ± 1 day, 27 ± 3 days, 55 ± 3 days, day from vaccination to challenge

> 6 weeks, but less than 6 months. The windows for follow-up visits post-challenge confinement period will be 27 ± 3 days and/ or 6 months post-vaccination (180 ± 14 days) whichever is longer.

7.1.1 *Screening Period*

Screening

Screening for eligible and consenting participants will be performed within approximately 6 weeks prior to randomization/the first administration of study drugs. It will be possible to include participants who are screened with the appropriate MNT assay from another protocol or screening test, but the test needs to be performed or repeated within 6 weeks of vaccination.

Some eligibility criteria will be checked prior to assessing MNT in the study. These criteria involve:

- life style questions i.e. smoking, contraception, identify current BMI (upon Investigator discretion), recent or planned participation in other studies etc. [inclusion criteria 1 to 4 and exclusion criteria 1 & 7].
- current illnesses including current medication.

Any physical examination, vital signs and laboratory assessments will be completed at Screening 2 visit within the 3 weeks leading to the vaccination once MNT is confirmed. However, in order to ensure a sufficient number of participants are vaccinated in a given group, MNT may be performed at Screening 2 at the same time as Screening 2 assessments.

Participants will be given a full explanation of the nature of the study and written informed consent (approved by the local ethics committee) will be obtained according to local requirements before any study-related assessment is carried out.

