7.2.3 Clinical Laboratory Tests

Blood samples will be collected by venipuncture at the time points indicated in the Time and Events Schedule. Biochemistry and haematology testing will be performed on these samples, as well as immunology testing (HBsAg, anti-HCV, and HIV antibodies) on the sample from screening. In female participants of childbearing

potential, human chorionic gonadotropin (hCG) using serum pregnancy test will be performed at screening and urine pregnancy test at the other study visits as per the Time and Event Schedule.

Standard laboratory tests will be performed by ZNA Klinisch Laboratorium. The following biochemistry and haematology tests will be performed on the safety blood and laboratory samples:

- Biochemistry: creatinine, glucose, aspartate aminotransferase (AST), alanine aminotransferase (ALT), alkaline phosphatase (ALP), gamma glutamylaminotransferase (GGT), C-reactive protein (CRP), bilirubin, sodium and potassium. Sodium and potassium tests are only required in the challenge period.
- Haematology: haemoglobin, haematocrit, red blood cell (RBC) count, white blood cell (WBC) count with differential, platelet count, mean corpuscular haemoglobin (MCH), mean corpuscular haemoglobin concentration (MCHC), mean corpuscular volume (MCV)

A urine drug screen for amphetamines, barbiturates, benzodiazepines, cannabinoids, cocaine, and opiates will be performed at screening visit 2 and upon admission at the clinical site (Period 1 & 2). A urine drug screen may be repeated to check false positive results.

An alcohol breath test will be performed at screening visit 2 and upon admission at the clinical site on Day 1 for Period 1 and on Day -2 (or Day -1) for Period 2. An alcohol breath test may be repeated to check false positive results.

The Investigator must review the laboratory results, document this review, and record any change occurring during the study he/she considers to be clinically relevant in the AE section of the eSource. Laboratory values outside the normal range will be flagged and their clinical relevance and significance will be assessed, documented and signed by the Investigator. A copy of all laboratory reports must be filed in the participant's records. These tests may be repeated at the Investigator's discretion.

7.2.4 *Vital Signs*

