RBC	red blood cells

	Statistical Analysis Plan	
FLU010	Final analysis	Final 3.0 of 15JUN2020

RND	all randomised subjects analysis set
SAE	serious adverse event
SAP	statistical analysis plan
SAF	safety analysis set
SCR	all screened subjects analysis set
SFC	spot-forming colony
SGS LS	SGS Life Sciences
SOP	standard operating procedure
SSC	symptom score card
STAT	statistics
TEAE	treatment-emergent adverse event
TOEP(H)	(heterogeneous) Toeplitz
UN	unstructured
vAUC	viral area under the curve (as determined by qPCR)
WBC	white blood cells
WI	work instruction

	Statistical Analysis Plan	
FLU010	Final analysis	Final 3.0 of 15JUN2020

DEFINITION OF TERMS

case report form (CRF)	A printed, optical, or electronic document designed to record protocol required information to be reported to the sponsor for each trial subject.
display	Analysis table, figure or listing
phase	Interval of time in the planned conduct of a study associated with a specific purpose: for example, screening, treatment, follow-up.
study drug	Pharmaceutical form of an active ingredient or placebo, being tested or used as a reference in a clinical study.
treatment-emergent abnormality	Any post-baseline abnormality that was not present at baseline (e.g. haemoglobin normal at baseline and grade 1 post-baseline; glucose grade 1 at baseline and grade 3 post-baseline). Abnormalities in vaccination phase are evaluated versus vaccination baseline. Post-challenge abnormalities are evaluated versus challenge baseline.
Within 2 consecutive days	Whenever in the endpoint definition it is mentioned that two positive samples/symptoms have to occur 'within 2 consecutive days', this includes the following cases:

Day x am	Day x pm	Day x+1 am	Day x+1 pm	
pos	pos	neg	neg	Two consecutive + on the same day
neg	pos	pos	neg	Two consecutive + on consecutive days
pos	neg	neg	pos	Two + on two consecutive days with intermittent - sample(s)

	Statistical Analysis Plan	
FLU010	Final analysis	Final 3.0 of 15JUN2020

TABLE OF CONTENTS

Signature page	2
Protocol history	3
List of abbreviations	4
Definition of terms	6
Table of contents	7
1. Introduction	11
1.1 Study objectives.....	11
1.2 Study design	12
1.3 Expected sample size.....	12
1.4 Randomisation and blinding.....	13
1.5 Interim analysis	13
1.6 Software.....	13
1.7 Validation model	14
2. Efficacy and immunogenicity analyses	15
2.1 Efficacy.....	15
2.1.1 Available data.....	15
2.1.2 Endpoints and derivation rules.....	16
2.1.2.1 Primary endpoint.....	16

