 - study discontinuation/completion date – AE start date + 1 day (when the AE start date is fully known but the AE is not resolved at the end of the study)

In this case the duration will be presented as “>x days”, x being the duration of the AE calculated by the end of the study.

3.1.3 *Presentation of results*

Tables will present TEAEs only. Pre-treatment AEs and follow-up AEs will only be listed. All tables will be presented by analysis phase (vaccination / challenge).

Analysis phases are defined in section 5.2.1.

	Statistical Analysis Plan	
FLU010	Final analysis	Final 3.0 of 15JUN2020

An overview table will show the number and percentage of participants with at least one event and the number of events for the following:

- TEAEs
- Solicited symptoms
- TEAEs or solicited symptoms
- Local solicited symptoms
- Local grade 3 solicited symptoms
- Systemic solicited symptoms
- Systemic grade 3 solicited symptoms
- Treatment-emergent AESI
- Serious TEAEs
- Non-serious TEAEs
- Grade ≥ 3 TEAEs
- Treatment-emergent grade ≥ 3 laboratory toxicity (see section 3.2.2)
- Fatal TEAEs
- TEAEs related to treatment (vaccination phase)
- TEAEs related to challenge (challenge phase)
- Serious TEAEs related to treatment (vaccination phase)
- Serious TEAEs related to challenge (challenge phase)
- Grade ≥ 3 TEAEs related to treatment (vaccination phase)
- Grade ≥ 3 TEAEs related to challenge (challenge phase)
- TEAEs for which the study was discontinued

Summary tables by MedDRA system organ class and preferred term will show the number and percentage of subjects with at least one event. The table of TEAEs will additionally show the number of events.

Separate tables will be prepared for the following:

- TEAEs
- Treatment-emergent AESI
- Serious TEAEs
- Non-serious TEAEs
- Grade ≥ 3 TEAEs
- TEAEs by worst severity
- Treatment related TEAEs
- Serious treatment related TEAEs
- TEAEs for which the study was discontinued

A summary table by symptom will show the number and percentage of participants with at least one symptom, overall, by type (local/systemic) and by symptom. The

	Statistical Analysis Plan	
FLU010	Final analysis	Final 3.0 of 15JUN2020

table of solicited symptoms will additionally show the number of events. Distinct tables will be prepared for the following:

- solicited symptoms
- grade 3 solicited symptoms
- solicited symptoms by worst severity

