5.2 PHASES AND TIME POINTS

5.2.1 *Phases*

All events and assessments will be allocated to phases.

Phase	Start	End
Screening	Date of signing the ICF, with 00:00 added as time part	Vaccination date(time) – 1 minute
Vaccination	Vaccination date(time)	Challenge date(time) – 1 minute
Challenge	Challenge date(time)	End date of Day 28 post-challenge visit, with 23:59 added as time part
Follow-up	End of challenge phase + 1 minute	Date of last contact, with 23:59 added as time part

Per definition, and for each subject, the last available phase ends on the date of last contact (or the cut-off date for the topline analysis), with 23:59 added as time part.

AEs will be allocated to phases as described in section 3.1.2. All other assessments will be allocated to phases based on the assessment date(time).

In case of (partially) missing date(time) fields which cannot be allocated to a phase based on the available date(time) information, the visit label will be used to allocate to the correct phase. If this is not possible (unscheduled visits or visits on a turning point between phases), assessments will be allocated to the vaccination phase unless the available parts of the assessments start or stop date(time) provide evidence for allocating to the challenge/screening/follow-up phase.

5.2.2 *Baseline and change from baseline*

Baseline will be defined by phase.

The vaccination baseline value is the last available and non-missing value before the first administration of any study drug and will be used for data collected during the vaccination period.

The challenge baseline value is the last available and non-missing value before the administration of challenge inoculation and will be used for data collected during the challenge period.

Change from baseline is defined as follows:

Change from baseline at time point t = value at time point t – baseline value.

	Statistical Analysis Plan	
FLU010	Final analysis	Final 3.0 of 15JUN2020

5.2.3 *Relative day*

Relative days (DY) will be calculated both with respect to the vaccination and to the challenge, according to the following rule:

- Concerned date < reference date: DY = concerned date – reference date
- Concerned date \geq reference date: DY = concerned date – reference date + 1

The reference dates are the vaccination date and the date of challenge.

5.2.4 *Analysis visits*

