5.4 PRESENTATION OF RESULTS

5.4.1 *Calculation of descriptive statistics and percentages*

For continuous parameters, full descriptive statistics will only be presented if there are at least 2 non-missing observations. Alternatively, only the number of non-missing data points and mean are shown.

Descriptive statistics will include the number of non-missing data points, the arithmetic mean, the standard deviation (SD), the median, minimum and maximum.

Descriptive statistics of efficacy parameters will additionally include standard error (SE) and 95% confidence interval (CI) on the mean (based on t-distribution, without continuity correction). Descriptive statistics of antibody response will show geometric mean and corresponding 95% confidence interval (CI) rather than arithmetic mean. Geometric mean and CI are calculated as the exponentials of the arithmetic mean and corresponding CI (based on t-distribution, without continuity correction) of the log-transformed data. Descriptive statistics of T cell response will show 95% CI on the median (based on ranks) and not on the mean.

Survival estimates will include the arithmetic mean with its SE, the median, first and third quartiles with their 95% CI, and the number of subjects who are assessed, censored and who have an event.

Mean, median, SE, SD and CI will be presented with one more decimal place than the individual values, with a maximum of 5 decimal places. Minimum and maximum will be presented with the same number of decimal places than the individual values, with a maximum of 4 decimal places.

P-values will be presented with four decimal places, ratios with three decimal places and test statistics with two decimal places.

For event-type data, the denominator will be all subjects in the analysis set and phase, unless specified otherwise, in which cases a footnote to the table will specify the denominator. All treatments will be shown, even if no events are present.

For frequency tabulations and cross-tabulations, missing values will not be included in the denominator count when computing percentages. For cross-tabulations of post-baseline results versus baseline results, a 'missing' category will be shown for baseline results if applicable.

Percentages will be shown with one decimal place.

5.4.2 *Presentation of treatments*

The following treatment labels will be used in the tables, listings and figures:

- PLACEBO
- MVA-NP+M1
- OVERALL

	Statistical Analysis Plan	

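### The vaccination-phase row for grade 3 or higher laboratory toxicity rests on one scheduled sample about 6 weeks or more after the dose, and its denominator includes participants with no scheduled test

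*SAP*

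**What the plan says.** SAP 3.1.3 lists the rows of the overview table, one of which is treatment-emergent grade 3 or higher "laboratory toxicity (see section 3.2.2"). The same section says "All tables will be presented by analysis phase (vaccination / challenge"). Neighbouring rows on relatedness are each tied to one phase. This row is not, so it is produced for both.

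SAP 5.2.1 ends the vaccination phase at "Challenge date(time) – 1 minute" and adds, for data other than adverse events, "All other assessments will be allocated to phases based on the assessment date(time"). The SAP's definition of a treatment-emergent abnormality states: "Abnormalities in vaccination phase are evaluated versus vaccination baseline". SAP 5.4.1 sets the denominator: "For event-type data, the denominator will be all subjects in the analysis set and phase, unless specified otherwise". It allows a different denominator if a table footnote gives it, but none is given for this row.

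On sampling, Protocol 7.1.1 says: "Any physical examination, vital signs and laboratory assessments will be completed at Screening 2 visit within the 3 weeks leading to the vaccination". The Period 1 schedule (Protocol Time and Events Schedule, repeated in SAP 9.4.1) marks haematology and biochemistry at Screening 2 and at unscheduled visits only. The next scheduled safety blood is in Period 2, on Day -2 or Day -1 before challenge. Protocol 7.2.3 adds: "Sodium and potassium tests are only required in the challenge period".

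**The concern.** A reader of the overview table will see a percentage in a vaccination-phase column and may take it as a statement about laboratory effects of the vaccine. The plan gives that reader two things to trip over. First, the number depends almost wholly on one late sample, so it says little about the days and weeks in which a short-lived reaction to vaccination would appear. Second, participants who are vaccinated but never challenged have no scheduled post-dose laboratory test, yet they are counted as if tested and found free of toxicity. Neither fact is visible in the row.

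A smaller gap concerns sodium and potassium. They are not scheduled before vaccination, so a severe value on Day -2 or Day -1 has no vaccination baseline to be compared with. The SAP does not say whether such a value counts as treatment-emergent.

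**Working it through.** **Planned numbers.** Protocol Table 2 gives 80 (+13) for MVA-NP+M1 and 54 (+8) for placebo. Then 80 + 13 = 93, 54 + 8 = 62, 93 + 62 = 155 vaccinated and 80 + 54 = 134 challenged, which reproduces the stated totals. Not challenged: 155 − 134 = 21.

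**When the row is informed.** Period 1 has no haematology or biochemistry on Day 2, Day 8, Day 28, Day 56 or at Month 6; the Day 8 and Day 28 blood is for immunogenicity and transcriptomics. Protocol 7.1 puts challenge more than 6 weeks and less than 6 months after vaccination. With challenge at 42 days, Day -2 or Day -1 falls at 42 − 2 = 40 or 42 − 1 = 41 days after the dose. With challenge near 180 days it falls near 178. By date and time this sample belongs to the vaccination phase, and it is the only scheduled post-dose safety blood there. An abnormality starting 8 days after vaccination would have to last at least 40 − 8 = 32 days to be present at the earliest scheduled sample.

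**Who is in the denominator without a scheduled test.** For unchallenged participants the vaccination phase runs to last contact (SAP 5.2.1), so they stay in the set and phase.

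| | Not challenged / vaccinated | Share |
|---|---|---|
| MVA-NP+M1 | 13 / 93 | 14.0% |
| Placebo | 8 / 62 | 12.9% |
| Both, at plan | 21 / 155 | 13.5% |
| Both, at the worst case in Protocol 9.2 (72 + 48 = 120 challenged) | 35 / 155 | 22.6% |

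**Dilution.** Printed percentage = rate among tested × tested / all. For an illustrative 10% among the tested: 10% × 134/155 = 8.6% overall, 10% × 80/93 = 8.6% for vaccine and 10% × 54/62 = 8.7% for placebo. With no events in the vaccine arm, the one-sided 95% upper bound 1 − 0.05^(1/n) is 3.7% for n = 80 and 3.2% for n = 93. The plan calls for no such bound; it only shows the scale.

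**Timing compared with dilution.** Assume a true incidence of 3% in vaccine recipients. The chance of at least one case is 1 − (1 − p)^n.

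- All 93 tested while the abnormality is present: 94.1%.
- 80 tested, all cases persisting to the pre-challenge sample: 91.3%.
- 80 tested, with 50%, 25% or 10% of cases persisting (p = 1.5%, 0.75%, 0.3%): 70.2%, 45.2%, 21.4%.

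The persistence shares are assumptions. They show that late sampling limits the row much more than the missing participants do.

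**The case against.** A reader might infer that the row is bound to look reassuring, or is forced towards zero. The documents do not support that. The Day -2 or Day -1 result counts, investigators may order haematology and biochemistry at unscheduled visits, and SAP 5.2.5 includes unscheduled values in the worst case for each phase. A participant admitted on Day -2 and then excluded may also have been sampled. So the accurate phrase is no *scheduled* result, at planned numbers.

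A reader might also infer a distorted comparison between arms. The schedule is the same for both and the untested shares are close, 14.0% and 12.9%, so the contrast is barely affected.

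The main laboratory displays (SAP 3.2.3, Tables 14.3.2.1 to 14.3.2.4) are by visit. For cross-tabulations SAP 5.4.1 leaves missing values out of percentages and shows a missing category for baseline. The thin testing will be visible there. This stands, but it does not correct the overview row, which follows the event-type rule.

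Finally, the absence of early safety bloods is a protocol choice shown openly in both documents, and SAP wording cannot supply the data. That also stands. What the SAP can do is stop the row from being read as if those weeks had been observed.

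**Conclusion.** The point holds as a minor matter of descriptive safety reporting. The vaccination-phase percentage is diluted by a factor of 134/155 at plan, and the row is uninformative about transient laboratory changes in roughly the first 40 days unless an unscheduled test was done. Safety data are summarised descriptively, and no endpoint or halting rule depends on this row.

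The conclusion rests on three assumptions. The row is event-type data under SAP 5.4.1, which fits a table counting participants with at least one event. The numbers challenged are as planned. The row uses the SAP 5.2.5 worst case, although SAP 5.2.4 says unscheduled results are only listed; without them, the row would rest on the single pre-challenge sample.

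It does not follow that the row should be removed, or that sodium and potassium should be left out. Either step could hide a real grade 3 or higher value.

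**What to change.** Keep the row in SAP 3.1.3 and change its vaccination-phase column as follows.

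- Use as denominator the participants with at least one post-vaccination, pre-challenge laboratory result, and print that number by arm. SAP 5.4.1 already provides for a footnoted denominator.
- Add a footnote such as: *Scheduled sample taken before challenge, about 6 weeks or more after vaccination; unscheduled results included.*
- Report any pre-challenge grade 3 or higher sodium or potassium value on a separate line marked *no vaccination baseline*, neither counted as treatment-emergent nor dropped.
- State in the clinical study report that laboratory effects in the weeks after vaccination were not systematically assessed.

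Leave the challenge-phase row as planned. The cost is one denominator, two short notes and one sentence in the report, with no new data. At planned numbers, if every event arises among challenged participants, the printed vaccine percentage rises by a factor of 93/80 = 1.16 and the placebo percentage by 62/54 = 1.15.

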Because of the potential for severe illness, efforts to minimise this risk are to be implemented during all clinical studies with this challenge strain. First, all prospective participants will be carefully evaluated for the presence of any known risk factor for severe influenza illness, including underlying pulmonary and cardiac disease, pregnancy, and/or immunosuppressive conditions; individuals with such conditions will be excluded from participation. Secondly, all enrolled participants will be continuously monitored under quarantine by trained and suitably accredited clinical staff for the duration of the study, with qualified physicians available as needed 24h a day. Thirdly, the challenge strain has been confirmed to be susceptible to the standard of care antiviral agents oseltamivir and zanamivir, in the event that the severity of the illness warrants rescue therapy.

Because the challenge virus preparation contains egg protein, individuals with known or suspected egg allergies should not participate, nor should individuals with a prior history of Guillain-Barré syndrome.

There is a theoretical risk that inducing influenza-specific T cells might exacerbate disease following challenge. No such worsening was observed in the 430 elderly participants who received QIV and MVA-NP+M1 in a recent study in the UK.

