3. SAFETY ANALYSES

3.1 ADVERSE EVENTS AND SOLICITED SYMPTOMS

3.1.1 *Available data*

Unsolicited adverse events (AEs) are coded into system organ classes and preferred terms using the medical dictionary for regulatory activities (MedDRA). For each AE, start and stop dates and times are collected as well as severity (grade 1 to grade 5), a seriousness flag, an AE of special interest (AESI) flag (i.e. events which could have an autoimmune origin), treatment relatedness (both to treatment and challenge agent), action taken towards the study drug and outcome.

The following solicited symptoms will be collected:

- Day 1 to Day 7 following vaccination (patient diary):
 - Local symptoms: pain, redness, induration (swelling), warmth, pruritis (itching)
 - Systemic symptoms: feverishness, chills, fatigue, myalgia/arthralgia (muscle/joint pain), headache, nausea, malaise, temperature
- Day 1 to Day 11 following challenge (SSC):
 - Local symptoms: nasal congestion (blocked nose), runny nose, sneezing frequency, sinus pressure/pain or facial pain, sore throat, difficulty swallowing, teary/watery eyes, painful eyes, aversion to light, dry cough, productive (wet) cough, difficulty breathing/tight chest
 - Systemic symptoms: dizziness, head congestion, headache, muscle aches, feverish, chills or shivering, lack of appetite, felt cold, sweating, nausea, stomach ache, vomiting, diarrhoea, tiredness/weakness, sleeping more than usual, lymphadenopathy

The following symptoms will only be questions if at least 2 other symptoms with grade 2 or higher are present: nausea, stomach ache, vomiting, diarrhoea, tiredness/weakness, sleeping more than usual.

Solicited symptoms clearly not related to the treatment/challenge are captured as adverse events in the clinical database. Therefore, events captured as solicited symptoms in the clinical database are always considered (at least possibly) related to the treatment/challenge. Each symptom's severity is graded from 0 (absent) to 3 (grade 3 - severe), except for redness and temperature, which are reported in mm for longest diameter and °C respectively.

	Statistical Analysis Plan	
FLU010	Final analysis	Final 3.0 of 15JUN2020

3.1.2 *Derivation rules*

Redness and temperature will be graded as follows:

Grade	Redness (mm)	Temperature (°C)
Normal (0)	< 25	< 38.0
Grade 1	25-50	38.0-38.4
Grade 2	51-100	38.5-38.9
Grade 3	> 100	39.0-40.0
Grade 4		> 40.0

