Treatment-emergent adverse events (TEAE) are defined as AEs starting during or after first administration of any study drug. Treatment-emergent (TE) solicited symptoms are defined as solicited symptoms reported from Day 1 on.

Based on their start date and time, AEs will be allocated to the phase during which they started. Each AE will therefore be reported in only one phase. (See section 5.2.1 for further information about study phases). In case the AE start date or time is incomplete or missing and the AE could consequently be allocated to more than one phase, the AE will be allocated to the treatment phase unless the available parts of the AE start or stop date(time) provide evidence for allocating to the non-treatment phase (screening / challenge / follow-up).

Some of the final safety presentations will include the number of reported events during the trial's analysis phases, not only the number of subjects who reported at least one event. Any change in AE severity is reflected by a new AE record being entered in the safety database. As such, the number of events could be inadvertently overreported due to the way in which AE records are captured within the safety database.

Overlapping/consecutive (unsolicited) events are defined as events occurring in the same subject with the same MedDRA preferred term and primary system organ class that have at least one day overlap or for which the start date of an event is one day

	Statistical Analysis Plan	
FLU010	Final analysis	Final 3.0 of 15JUN2020

after the end date of the preceding event. Overlapping/consecutive events may be combined into one AE or not, according to the following rules:

- In case overlapping/consecutive events start within a single phase (see section 5.2.1 for further information about study phases.), they are considered as one and the same AE. The individual events that contribute to this AE are retained as individual records in the ADaM database but are assigned the same onset, end, phase and total duration. They are counted/presented as one event in TLFs.
- In case overlapping/consecutive events start both in the challenge phase and in the follow-up phase, they are allocated to the active phase only (challenge phase) and are considered as one and the same AE. The individual events that contribute to this AE are retained as individual records in the ADaM database but are assigned the same onset, end, phase and total duration. They are counted/presented as one event in TLFs.

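### The adverse event overview counts vaccine-related events in the vaccination phase only, so one that starts after inoculation is in no vaccine-related row

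*SAP*

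**What the plan says.** SAP 3.1.1 lists, among the items collected for every unsolicited adverse event, "treatment relatedness (both to treatment and challenge agent"). SAP 3.1.2 gives the allocation rule: "Based on their start date and time, AEs will be allocated to the phase during which they started. Each AE will therefore be reported in" one phase only. Under SAP 5.2.1 the vaccination phase ends one minute before inoculation, and the challenge phase runs from inoculation to the Day 28 post-challenge visit.

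The overview table in SAP 3.1.3 has three vaccine-attribution rows: "TEAEs related to treatment (vaccination phase"), "Serious TEAEs related to treatment (vaccination phase") and "Grade ≥ 3 TEAEs related to treatment (vaccination phase"). The challenge-attribution rows mirror them, for example "Serious TEAEs related to challenge (challenge phase") and "Grade ≥ 3 TEAEs related to challenge (challenge phase").

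The tables by system organ class and preferred term include one for treatment-related TEAEs (14.3.1.7) and one for serious treatment-related TEAEs (14.3.1.8). Neither title names a phase, and SAP 3.1.3 presents all adverse event tables by phase. Events in the later follow-up phase are only listed.

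**The concern.** Protocol 2.2 makes the safety of vaccination, and the safety of challenge after vaccination, secondary objectives. Protocol 9.1.3 asks that the summaries cover related events and events following challenge. Protocol 7.2.1 also names a vaccine effect that could appear only after inoculation: "There is a theoretical risk that inducing influenza-specific T cells might exacerbate disease following challenge".

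An investigator can therefore record, after challenge, that an event is possibly related to the vaccine, and the database will hold that judgement. The overview, which is where many readers look first for vaccine-related and serious vaccine-related counts, has no row for it. A zero in the serious vaccine-related row would describe only the period before inoculation, although it could be read as describing the whole trial. With rare events, one event is enough to change that reading.

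**Working it through.** No stated figure needs reproducing; the point concerns table structure. The check traces one hypothetical record through the SAP rules.

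**Record.** A serious Grade 3 myocarditis starts on challenge Day 5 and is judged possibly related to both the vaccine and the challenge agent. Myocarditis is an event of special interest (Protocol Appendix 1). Under SAP 3.1.2, at least possibly related counts as related.

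**Step 1, phase.** The start time falls after inoculation, so the event belongs to the challenge phase and to no other (SAP 3.1.2, 5.2.1).

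**Step 2, planned displays.**

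| Display | Is the event counted? |
|---|---|
| Overview, challenge phase: TEAE, serious, Grade ≥ 3 and AESI rows | Yes, without a causality filter |
| Overview: three challenge-related rows | Yes, in all three |
| Overview: three vaccine-related rows | No, restricted to the vaccination phase |
| Tables 14.3.1.3 (AESI), 14.3.1.4 (serious), 14.3.1.6 (Grade ≥ 3) | Yes, without a causality filter |
| Tables 14.3.1.7 and 14.3.1.8, challenge phase | Yes, but which attribution they show is not stated |
| Listings 16.2.7.1 (all) and 16.2.7.2 (serious) | Yes |

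If the same event were judged related to the vaccine alone, it would drop out of the challenge-related rows as well and would appear in no related row of the overview.

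**Step 3, what treatment related can mean in 14.3.1.7 and 14.3.1.8.** The dichotomy in SAP 3.1.2 does not separate the two causality judgements, and the worked example there carries a single relatedness variable for a challenge-phase event. Three readings are open. The table shows how many of the three vaccine-related counts (all, serious, Grade ≥ 3) are available for the challenge phase under each.

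| Reading | Overview | Tables 14.3.1.7 and 14.3.1.8 | Counts available |
|---|---|---|---|
| Vaccine | 0 | 2 (all, serious) | 2 of 3 |
| Challenge agent | 0 | 0 | 0 of 3 |
| Either product | 0 | 0 separable from challenge-related | 0 of 3 |

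No table of related Grade ≥ 3 events by system organ class is planned (SAP 3.1.3 and 8.1), so that count is missing under every reading.

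**Step 4, limits.** Participants who are vaccinated but never challenged are unaffected, because their last available phase runs to last contact (SAP 5.2.1). The mirror restriction costs nothing before inoculation, since no event can then be related to the challenge agent.

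**The case against.** The strongest reply is that the SAP already provides the missing counts. SAP 3.1.1 sets treatment against challenge agent, and the overview rows use the same contrast. Read consistently, the challenge-phase panels of Tables 14.3.1.7 and 14.3.1.8 would show vaccine-related events while the overview shows challenge-related ones. The myocarditis example would then appear in 14.3.1.8. This reading is plausible, and it rules out the stronger inference a reader might draw, that one of the two attributions is always missing from the tables in the challenge phase. The documents do not support that inference. They also do not confirm the favourable reading, and it would not supply the Grade ≥ 3 count.

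The second reply is that enhanced disease in a randomised, blinded trial is judged mainly by comparing arms and not by a blinded investigator's causality opinion. This stands. The challenge-phase TEAE, serious, Grade ≥ 3, fatal, AESI and solicited-symptom counts are shown by arm without a causality filter, and symptom scores and viral load are compared as efficacy outcomes. A reader might infer that the plan could not reveal enhanced disease; the planned displays show otherwise.

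The third reply is that nothing is lost, because all events are listed and serious events have their own table and listing. This also stands, but a listing does not replace a count in a summary table.

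**Conclusion.** The point holds as a gap in the tabulation of causality, of minor weight. Three overview rows (all, serious and Grade ≥ 3 vaccine-related TEAEs) leave out every event that starts after inoculation. For the challenge phase, the Grade ≥ 3 count is in no planned table; the other two are available only if Tables 14.3.1.7 and 14.3.1.8 are defined by relatedness to the vaccine.

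The number of events affected cannot be known in advance and may be zero. A share of follow-up days would not measure it: that share is a length of time, not a count of events, and it varies with a vaccination-to-challenge interval that Protocol 7.1 allows to run from over 6 weeks to under 6 months.

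No endpoint, test, analysis set or collected item is affected. The conclusion assumes that the phase labels in SAP 3.1.3 are applied as written.

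**What to change.** In SAP 3.1.3, add three rows to the challenge-phase overview beside the challenge-related rows: TEAEs, serious TEAEs and Grade ≥ 3 TEAEs related to the vaccine. For the challenge phase, present Tables 14.3.1.7 and 14.3.1.8 once by relatedness to the vaccine and once by relatedness to the challenge agent, and name the causality variable in each title. In SAP 3.1.2, state that the dichotomy is applied to each judgement separately.

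The cost is three overview rows, one more panel in each of two tables and one clarifying sentence. Both judgements are already collected, so no new data are needed.
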